- ii. **Potential Benefits:** Participants in the control group will not directly benefit. Participants in the intervention group will receive study visits from a Nurse, an Occupational Therapist, and a Handyman.

F2. Data Safety and Monitoring Plan

Please see the full DSMP included with this IRB package for additional information on the risks related to this study.

Early stopping rules: All Adverse events will be classified by severity and expectedness. Tracking reports will ensure that any statistically significant increases in death, hospitalization, or falls resulting in hospitalization are identified. Statistical tests of group difference will be conducted to determine if rates of serious adverse events differ between intervention and control groups. The DSMB will decide a threshold for the difference required between groups to consider stopping. Because there will be surveillance bias, as the control group participants will be much less likely to report adverse events on a regular basis, the DSMB may consider a difference in less than 50% increase in adverse events to be an acceptable difference.

G. Data Storage and Confidentiality

Data with identifiers will be used and stored by the research and intervention teams at VNSNY, all subject-identifying information on paper in the office will be kept in locked files accessible only to study staff at VNSNY, or, if in use in the field (assignment sheets to field interviewers and intervention staff), will be kept securely and destroyed at the earliest opportunity. Access to shared-drive network folders will be electronically restricted to the appropriate team members. Dates of birth and initials will be used along with the study IDs to confirm appropriate merging of data from different sources. All study staff have or will be thoroughly trained in the need to maintain strict confidentiality.

Legal Risks such as the risks that would be associated with a breach of confidentiality

In the unlikely event that a breach in confidentiality should occur, the study team will take the appropriate steps to inform the study participant and both VNS and Johns Hopkins University (JHU) IRBs that such an event has occurred.

Financial Risks

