This study is a single-masked, two-group, randomized trial to test the effectiveness of CAPABLE in reducing ADL difficulties compared to those randomized to usual care. The experimental group will receive CAPABLE services, which include visits from an Occupational Therapist, a Registered Nurse, and a licensed Handyman. The usual care group will not receive additional visits from study clinicians. All participants will be interviewed at 20 and 52 weeks post-baseline. Re-admission to skilled home health care, acute care hospitalization, skilled nursing facility, and nursing home admission will be assessed via VNSNY CHOICE claims data at 90 days (33 weeks) post follow up assessment. We will evaluate overall health care costs at 52 weeks (long-term impact). Outcome measures will be assessed by interviewers and analysts masked to treatment assignment and without interventionist contact.

STUDY PROTOCOL

A. Purpose and Specific Aims

The overall goal of this rigorous experimental study is to test the effectiveness of a multi-component homebased intervention to enhance physical function of patients who have ADL difficulties and have been recently hospitalized. We will conduct a pragmatic effectiveness trial in the skilled home health setting to evaluate CAPABLE in approx. 268 racially and ethnically diverse older adults with ADL difficulties following hospitalization and skilled home health care.

Primary Aim:

Hypothesis: those receiving CAPABLE will have fewer ADL difficulties

- 1) Test the effectiveness of CAPABLE in reducing the number of ADLs performed with difficulty at 20 weeks post-randomization
- 2) Estimate CAPABLE's economic impact on subsequent health care utilization and costs over 52 weeks post-randomization compared to CAPABLE program cost.

Secondary Aim:

- 1) Testing CAPABLE effectiveness on ADL function at 52 weeks
- 2) Testing effects for key subgroups (gender, ethnicity)
- 3) Examining theoretically-driven mediation pathways for treatment mechanisms

B. Background

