The usual care group will not receive additional visits from study clinicians. All participants will be re-evaluated at 20 and 52 weeks. Re-admission to skilled home health care, acute care hospitalization, skilled nursing facility, and nursing home admission will be assessed via VNSNY CHOICE claims data at 90 days (33 weeks) post follow up assessment. We will evaluate overall health care costs at 52 weeks (long-term impact). Outcome measures will be assessed by interviewers and analysts masked to treatment assignment and without interventionist contact. Each design component is described below.

Figure 1: Study Flow

C2. Characteristics of study population

Participants will be community dwelling older adults who agree to participate in the study. We will enroll approx. 268 patients over a 3 year period, enrolling about 100 participants per year. Eligible patients will be VNSNY CHOICE Medicare Advantage Health Plan members who received skilled home health care following an acute hospitalization. We will recruit 60 days after the hospital discharge so that we are capturing residual ADL difficulty after the initial healing and strengthening has occurred. Inclusion criteria include: 1) age 65 or older; 2) 60 days after an acute care hospitalization followed by VNSNY home care episode; 3) Difficulty with at least 1 ADL; 4) Member of the VNSNY CHOICE Medicare Advantage Health Plan; 5) Are able to stand with or without assistance; 6) Are available during the study timeframe. Exclusion criteria includes: 1) Significant cognitive impairment based on the Callahan 6-item cognitive screening tool; 2) Does not speak English or Spanish as their primary language; 3) Is actively receiving cancer treatment; 4) Plans to move in less than 1 year.

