We will recruit CAPABLE participants from the Visiting Nurse Service of New York VNSNY CHOICE Medicare Advantage Health Plan. VNSNY CHOICE Health Plan is a non-profit managed care organization that helps people remain in their homes rather than moving to nursing facilities. VNSNY CHOICE builds on VNSNY's expertise in coordinating all the health and support services that older and frail New York residents need to stay healthy and independent in their own homes. Selecting participants from this population allows us to target lower-income, Hispanic, and African American older adults from four New York City boroughs, including Manhattan, Brooklyn, Queens, and the Bronx. Preliminary analyses revealed that a large proportion of health plan members experienced a loss of functioning following their stay in hospitalization and home care (41%; n=615) and most had at least some remaining level of activity limitations at the time they were discharged from home care (92%; n=1,382).

C3. Intervention

C3.1. CAPABLE Program

CAPABLE is informed by theory and evidence-based practices. It involves up to 10 home sessions each of 60 minutes duration over a 5-month period. It draws upon clinical approaches to enhance uptake and adoption of intervention strategies by study participants such as patient-centered care and motivational interviewing. **Every participant receives each component of the intervention (assessment, goal setting, interactive problem-solving, and training) but interventionists clinically tailor content to each participant's functional goal.**

C3.2. Intervention Delivery Characteristics

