The consent form will be translated into Spanish and submitted the IRB once it is ready. A copy of the English consent form is attached with this IRB package.

C6. Randomization

After a home visit to consent and collect baseline data, patients will be randomized in a 1:1 ratio, to receive either: (1) CAPABLE intervention or (2) usual care. The schedule will be stratified by surgical vs. non-surgical hospital admission due to the marked difference in functional recovery.¹³ Cases will be randomized within variable-sized blocks from 4 to 8 participants. These procedures will maintain allocation concealment throughout the trial, consistent with the CONSORT recommendations.¹⁴ No research staff or investigator interacting with potential participants will be able to anticipate treatment allocation of the next assignment because of variable block sizes.

C7. Patient interviews

Study participants will be asked to participate in one interview at the start of the study, a second interview 20 weeks later and a possible third interview in about 52 weeks post study enrollment. Each interview visit will last about 1 hour. During each visit, a trained research interviewer will ask the participant questions about their daily activities, pain level, medical conditions and other questions about their health (see Table 1 below). At the very end of the study, after all of the interviews are completed, another member of the research team may call and speak to the patient briefly about how the study went. All study participants will receive \$25 after each completed in-home interview.

Table 1. Data Sources

MEASURES (CITATION)	MEASURED WHEN	CONSTRUCTS AND MEASUREMENT ATTRIBUTES	TESTED IN SPANISH SPEAKING POPULATIONS
Demographics	BL, 20, 52 weeks	Age, race, sex, insurance attributes, live with others, reason for hospital stay,	Yes
ADLS – Katz ^{72,73,75} 0-16	BL, 20,52 weeks	Bathing, dressing (upper and lower), toileting, transferring, toileting, feeding, walking across small room. Cronbach's alpha 0.87-0.94. ⁷⁷	Yes
IADL 0-16 ⁷⁶	BL, 20,52 weeks	Ability to use the telephone, shop, prepare food, light housekeeping, wash laundry, take own medication, travel independently, and manage finances	Yes
Prior hx ADLs, IADLs	BL	ADL and IADL assessment prior to hospitalization	Yes
PROMIS Global 10	BL, 20,52 weeks	Overall health, quality of life, social activities, self-care, pain, fatigue, anxiety/depression, and mobility	Yes ⁷⁷

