Home hazards-CDC Home Hazard Index 0-41	BL, 20 weeks	42 items- general household, kitchen, bathroom, bedroom and stairways. No psychometric data available.	Yes
Depression PHQ-9 ^{78,79} 0-27	BL, 20,52 weeks	Identification of Depression. Sensitivity 88%, specificity 78%	Yes ⁸⁰
Pain – Brief Pain Inventory ⁸¹	BL, 20,52 weeks	Severity of pain, impact of pain on daily function, location of pain, pain medications and amount of pain relief in the past week	Yes
Patient Activation ^{82,83}	BL, 20 weeks	General preventive behaviors, disease-specific behaviors, and health fatalism Reliability 0.89, Cronbach alpha 0.87. Test-Retest reliability 93%	Yes ⁸²
Control Strategy Use ^{84,85}	BL, 20 weeks	Behavioral and cognitive processes that facilitate adaptation to life challenges Cronbach alpha = 0.69	Not yet—will do psychometric testing in this study
Charlson Comordity Index ⁸⁶	BL, 20,52 weeks	Co-morbidity, will ascertain from medical record	From medical chart ^{86,87}
Readmission rates	BL, 33 weeks	Purpose-built data collection form to be collected by research team	Yes
Medical utilization and costs	BL, 52 weeks	Purpose-built data collection form to be collected by research team	Yes
Formal and informal care	BL, 20, 52 weeks	Helpers section from National Health and Aging Trends Study ⁸⁸	Yes

C8. Spanish Translation

All data collection materials such as the patient survey, consent form, screener and scripts will be translated into Spanish via a professional translation service. Spanish copies will be submitted to the IRB prior to recruiting Spanish speaking study participants.

D. Data to be employed

D1. Data Sources

Data will be collected from the following sources:

- VNSNY CHOICE Medicare Advantage electronic medical record
- VNSNY electronic health record administrative variables
- OASIS data (start of care, transfers, resumption of care and discharge)

- Telephone screening recruitment calls
- In-home interviews

D2. Data Collection and Management

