Field interviewers trained in quality data collection will directly enter data into the Redcap data entry and management system. With patient permission, the interviews will also be audiotaped. Intervention staff will also record periodic visits with patient permission. The project manager will check data from screening, intervention sessions, and final data collection for completeness and appropriateness and will listen to recordings based on quality control protocols. There will be a Data Safety and Monitoring Board (DSMB) of senior researchers external to the project with expertise in research methods, and older adults to assure subject safety and adherence to human subject protection policies. Evaluation will include periodic assessments of data quality, participant recruitment, accrual, and retention.

Participants are part of a Medicare Advantage (MA) Managed care plan. Claims from the VNSNY CHOICE Medicare Advantage database will be used to identify study participants who were admitted to a hospital (planned and unplanned), skilled nursing facility, and/or nursing home at 90 days and during the 52-week follow-up period. Services will be identified from claims using facility and Current Procedural Terminology (CPT) codes. We will use data from VNSNY administrative records to identify participants who were readmitted to skilled home health care during the follow-up period.

E. Analytic Methods

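### Does the 90-day admission readout leave out participants who miss the 20-week interview, and are the admission outcomes too loosely defined to analyse?

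*Combined protocol and SAP*

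**What the plan says.** Study Methods and C1 state that the four admission types "will be assessed via VNSNY CHOICE claims data at 90 days (33 weeks) post follow up assessment". Table 1 lists readmission rates at baseline and 33 weeks, with the entry "Purpose-built data collection form to be collected by research team". D2 uses plan claims to find admissions to hospital, skilled nursing facility or "nursing home at 90 days and during the 52-week follow-up period", and turns to VNSNY administrative records for skilled home health readmission.

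The horizon is set in Primary Aim 2, which concerns "economic impact on subsequent health care utilization and costs over 52 weeks post-randomization". E3, aim 2, analyses events at 52 weeks with proportional hazards models. Its list adds inpatient rehabilitation and does not name nursing home. The SAP section on secondary outcomes specifies Cox models with baseline covariates. It names nursing home, does not name inpatient rehabilitation, and gives no time window.

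C7 schedules a baseline interview, "a second interview 20 weeks later and a possible third interview in about 52 weeks post study enrollment". E1 states an intention-to-treat analysis of all participants. C3.4 says that service use will be taken from the electronic record for everyone in the study. Neither E3 nor the SAP says how death or leaving the health plan is handled in the event models.

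**The concern.** The phrase "at 90 days (33 weeks) post follow up assessment" ties the readout to an assessment that takes place after randomisation. D1 lists "In-home interviews" as a data source, so someone who has died or is in a facility at week 20 is likely to have no assessment and hence no date to count from. Leaving such people out would select on something that follows treatment and is related to the outcome itself.

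D2's 90 days has no stated start. Counted from baseline, it would end while CAPABLE is still being delivered, since C3.1 describes "up to 10 home sessions each of 60 minutes duration over a 5-month period".

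Skilled home health readmission comes from claims in C1 and from administrative records in D2, and the Table 1 form could be read as a third source. If that form relied on participant report, the surveillance bias acknowledged in F2 could produce more recorded events in the CAPABLE arm. Uneven event lists and silence on censoring would leave further choices until after the data are seen.

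**Working it through.** **Inputs.** Enrolment 268 (134 per arm), 200 expected with 20-week data, planned attrition 25%, earlier attrition 13% (all E2); assessments at 20 and 52 weeks (C7); readout at 90 days, labelled 33 weeks (C1).

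**The plan's own sample size.** A two-sample t-test for 0.40 SD, two-sided 0.05 and 80% power needs 100 per arm. Then 100 / 0.75 = 133.3, rounded up to 134, so 268 in total. This reproduces E2. The sample size is for the ADL score and does not depend on the admission outcomes.

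**Expected without a 20-week interview.** 268 − 200 = 68, and 68 / 268 = 25.4%. At 13%, 268 × 0.13 = 34.8, about 35. These are missed interviews, not missing claims.

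**What 33 weeks means.**
- 90 / 7 = 12.9 weeks, so 33 weeks is not a conversion of 90 days.
- Thirty-three weeks after the 20-week assessment would be week 53, beyond the 52-week follow-up.
- 20 + 90 / 7 = 32.9 weeks from baseline. This is the only reading that fits, and Table 1 gives week 33 in a column whose other entries are baseline, 20 and 52 weeks.

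Week 33 is therefore a fixed study date that every participant has, interviewed or not.

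**Is any follow-up uncovered?** If the 90 days were a window opening at the assessment, weeks 0 to 20 would fall outside it: 20 / 32.9 = 61%. But C1 says at 90 days, which is a time point. D2 also identifies facility admissions throughout the 52-week follow-up, and Aim 2 counts from randomisation. Weeks 0 to 20 are covered.

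**Does the event model need the 20-week interview?** The SAP's Cox model uses treatment group, baseline covariates and event times. Group and covariates are known at entry, and the event times come from claims or agency records. Nothing in it comes from the 20-week visit.

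**Sources.** C1 summarises all four events under claims. D2 is more specific: claims for facility admissions, administrative records for skilled home health. That is a real difference between two sources. The form is not a demonstrated third one. Its Table 1 row does not name skilled home health, and the row for utilization and costs carries the same form wording although E3 takes medical costs from claims. C7 also schedules no interview at week 33, which makes participant report unlikely.

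**Event lists.** Nursing home is in Study Methods, C1, D2 and the SAP but not in E3. Inpatient rehabilitation is only in E3. Both the E3 and SAP lists are introduced as examples, so they are uneven but do not contradict each other.

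**Size of any effect.** The documents give no event rate, hazard ratio or event count for admissions, so no bias or power figure can be calculated.

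**The case for a change.** The strongest case is that a programmer could build different windows from C1, D2 and Table 1. E1 makes complete cases the default for primary analyses, and utilization sits under a Primary Aim. Nothing says in so many words that a person without a 20-week interview stays in the admission readout. Deaths are expected, since E1 treats deceased cases separately when imputing. Plan membership is an entry criterion, yet nothing says what happens when it ends. E3's claims include home health, so the cost and event parts of one aim could count home health episodes from different records. Clearer wording would cost little.

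Part of this stands. The 90 days in D2 needs C1 to supply its start, the home health source differs between C1 and D2, the final event set is not fixed, and there is no written rule for death or disenrolment. The last is the most substantive omission.

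The exclusion does not stand. A complete case for a claims-based event model is a person with claims follow-up, not one with an interview, and C3.4 and E1 both point to including everyone. The self-report argument is conjecture: F2 concerns adverse-event reporting, and no section says admissions are self-reported. Preferring claims to administrative records for home health is a choice between two workable sources, and D2 has already made it.

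**Conclusion.** The concern does not call for a change. The 68 (or 35) participants are expected to miss an interview; the plan does not drop them from the admission analysis. The 61% uncovered window depends on a reading that D2 and Aim 2 rule out. What remains is unfinished detail that analysts would fill sensibly: week 33 and week 52 counted from baseline or randomisation for everyone, follow-up ended when plan membership ends, death handled by a standard method and reported as such, and the events listed as analysed.

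This rests on two assumptions: that week 33 is study time, which the arithmetic supports, and that claims continue for people who miss an interview but remain in the plan. No stated rule has been shown to give a wrong result. The SAP treats these events as secondary outcomes with descriptive p-values, and the ADL analysis, its error rate and its sample size are unaffected.

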E1. Analytic Approach. The overall goal of this rigorous experimental study is to test the effectiveness of a multi-component homebased intervention to enhance physical function of patients who have ADL difficulties and been recently hospitalized. We will use intention-to-treat analysis (ITT) as the primary method to analyze the results; data from all participants will be analyzed as members of their assigned study group. We may analyze post randomization data (e.g., treatment compliance) in supplementary analyses, such as complier-average causal effect (CACE) models. In addition to the primary outcome, numerous comparisons will be conducted for the secondary outcomes. P-values from these secondary outcomes will be considered descriptive indicators of the intervention impact, and not as absolute indicators for null hypothesis testing, which might require p-value adjustments for inflated type I error rate due to multiple comparisons. For our primary analyses, we will use cases with complete data. We will also conduct sensitivity analyses comparing the complete case analysis with analyses that use multiple imputation for missing data. Models will compare imputation done 1) for all people with missing data, including deceased cases, and 2) for only those who survived but dropped out.

E2. Sample Size

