Sample size calculations are based on our ability to detect clinically meaningful effect sizes for CAPABLE on the primary outcome of mean ADL difficulty score. All calculations are based on two-sided tests of 0.05 significance. Assuming a conservative attrition rate of 25% during the 20-week follow-up period, (we have consistently had 13% attrition in prior CAPABLE studies)¹⁰ we would need to enroll 60, 85, and 134 participants per treatment arm to detect, with 80% power, an intervention effect size of 0.60, 0.50, and 0.40, standard deviation units, respectively, at 20 weeks after baseline. Preliminary data showed a 41% reduction in ADL difficulty (*0.76 standard deviation units*) in the post-hospitalized group.¹⁰ Smaller effects of 0.57 to 0.60 standard deviation units were noted for other outcomes, and effect sizes of 0.63 for ADL difficulties and 0.62 for IADL difficulties were obtained in a small RCT pilot.¹⁵ By enrolling at least 268 participants, we anticipate having 20-week outcome data (primary endpoint) on 200 participants after 25% attrition. This sample size will provide excellent power to detect clinically meaningful differences between intervention and usual care groups.

E3. Primary study aims:

- 1. Test the effectiveness of CAPABLE in reducing ADL difficulties compared to usual care after 20 weeks of intervention.** We will address this aim using an analysis of covariance on the 20-week Katz summary disability score with treatment group as the primary independent variable and the baseline Katz score as the primary covariate. Other baseline demographic (e.g., gender) functional ability, and clinical variables (e.g., Charlson comorbidity index, pre-hospitalization ADL function) will be included as covariates if there are any random imbalances on those variables across intervention groups or if they are significantly correlated with the 20-week Katz score after adjustment for the baseline Katz score.

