The overall goal of this rigorous experimental study is to test the effectiveness of a multi-component home-based intervention to enhance physical function of patients who have ADL difficulties and have been recently hospitalized compared to a usual care control group. We will use an intention-to-treat (ITT) analysis to compare these two conditions; data from all participants will be analyzed as members of their randomly assigned treatment group. The primary outcome will be the Katz measure of difficulties with activities of daily living (ADLs). Scores on this measure range from 0 to 16, with higher scores indicating greater disability. In addition to the primary outcome, several additional comparisons will be conducted on secondary outcome variables. Because there is only one primary outcome measure, no adjustment for type I error is made for multiple comparisons, and a statistically significant finding will be indicated if the p-value is less than 0.05 for the treatment effect. This would indicate a type I error rate of less than 5% for rejecting the null hypothesis of no difference between treatment groups if the null hypothesis is, in fact, true. Two-tailed tests will be used for all statistical comparisons. P-values will also be reported for the secondary outcome analyses but these p-values from the secondary analyses will be considered descriptive indicators of the intervention impact on those measures and not as absolute indicators for null hypothesis testing.

Comparison Group Selection

This is a two group comparison. A total of 268 participants will be enrolled and randomized in a 1 to 1 ratio to either the intervention condition or to a usual care control group, with 200 participants expected to provide outcome data after accounting for 25% attrition. A total of 200 participants for analysis will provide 80% power to detect a clinically meaningful difference of 0.40 standard deviation units between intervention and usual care groups on the primary outcome measure of ADL difficulty.

Type of Statistical Test

This two group comparison will be a test of **superiority**. A two-tailed test will be used with the type I error rate set at 0.05.

Statistical Test of Hypothesis (Primary Outcome)

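### No planned 20-week ADL analysis counts death as an unfavourable outcome; the only one that includes participants who died imputes a Katz score for them

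*Combined protocol and SAP*

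**What the plan says.** Three planned analyses of the 20-week Katz score bear on participants who die first, all in section E1 (Analytic Approach):

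- The primary analysis uses complete cases, so anyone who dies before week 20 drops out.
- Sensitivity set 1 uses multiple imputation "for all people with missing data, including deceased cases".
- Sensitivity set 2 uses multiple imputation "for only those who survived but dropped out", so the deceased are left out again.

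E1 states no imputation model and no special value or shift for a death. The Statistical Analysis Overview says that "data from all participants will be analyzed as members of their randomly assigned treatment group" and specifies an ANCOVA on the 20-week score, but is silent on missing scores and on death. The time-to-event outcomes in E3 and in the Overview's secondary-outcome section are admissions; death is not among them. Death by arm appears in F2 (Data Safety and Monitoring Plan), as a safety comparison not linked to the ADL endpoint.

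**The concern.** A participant who dies before week 20 has no 20-week Katz score. The value does not exist, which differs from a score that a living participant failed to provide. Imputing it answers a hypothetical question: what function would have been had nobody died.

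In each of the three analyses a death is therefore either removed or replaced by a predicted living score. In none is it a bad result. A reader who saw the three estimates agree could take that as evidence that deaths do not affect the ADL conclusion, when the comparison has little ability to show such an effect. This matters most if deaths differ by arm. The participants are 65 or older, recently hospitalised and already limited in ADLs, and follow-up continues to 52 weeks, when more deaths will have accrued.

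**Working it through.** **The plan's own figures.** The sample size is not in dispute. E2 states "All calculations are based on two-sided tests of 0.05 significance" and "Assuming a conservative attrition rate of 25% during the 20-week follow-up period", against 13% in earlier studies. With n = 2(1.96 + 0.842)²/d² per arm, divided by 0.75:

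- d = 0.60: 44 analysed, 59 enrolled (stated 60)
- d = 0.50: 63 analysed, 84 enrolled (stated 85)
- d = 0.40: 99 analysed, 132 enrolled (stated 134)

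Also 268 × 0.75 = 201 (stated 200), and power with 100 per arm at 0.40 SD is 80.7% (stated 80%). The figures reproduce. Neither attrition figure separates deaths from dropout, so the documents supply no death rate. They give no Katz SD either.

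**Size of what the plan cannot show.** Let p_T and p_C be the proportions dead by week 20 in CAPABLE and usual care, and g the gap between the score used for a death and the survivor-like imputed score. If g is the same in both arms, counting deaths changes the difference (CAPABLE minus usual care, higher being worse) by (p_T − p_C) × g.

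Assumptions, none from the documents: SD 4, and imputed values 6 to 10 points below 16. The value 16 is used here only as a yardstick.

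- 3% versus 6%: 0.03 × 6 = 0.18 to 0.03 × 10 = 0.30 points. Divided by 4, this is 0.045 to 0.075 SD, or 11% to 19% of the 0.40 SD target.
- 3% versus 8%: 0.05 × 6 = 0.30 to 0.05 × 10 = 0.50 points, or 0.075 to 0.125 SD.
- With SD 3 instead, the first range becomes 0.18/3 = 0.06 to 0.30/3 = 0.10 SD.

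The sign follows the imbalance. More deaths under usual care would enlarge CAPABLE's apparent benefit; more deaths under CAPABLE would shrink it.

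**Simulation.** 134 per arm, 600 runs per row. Assumptions: baseline Katz mean 5 and SD 3, baseline slope 0.6, 12% random dropout among survivors, death likelier at higher baseline Katz, imputation from arm and baseline. The last column scores death as 16 and omits surviving dropouts. Estimates are in SD units; negative favours CAPABLE.

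| Deaths, CAPABLE / usual care | True benefit | Complete case | Set 1 | Set 2 | Death as 16 |
|---|---|---|---|---|---|
| 5% / 5% | 0 | 0.002 | 0.002 | 0.003 | −0.001 |
| 10% / 5% | 0 | −0.001 | 0.000 | −0.001 | 0.193 |
| 5% / 10% | 0 | 0.000 | −0.001 | 0.000 | −0.185 |
| 12% / 4% | 0 | −0.005 | −0.005 | −0.005 | 0.297 |
| 5% / 5% | 0.40 | −0.375 | −0.374 | −0.375 | −0.355 |
| 10% / 5% | 0.40 | −0.374 | −0.373 | −0.374 | −0.136 |
| 5% / 10% | 0.40 | −0.382 | −0.383 | −0.382 | −0.542 |

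The three planned analyses agree whatever the death rates. The last column moves with the imbalance and hardly at all when deaths are equal. In the equal-death row with a true benefit the shift is about 0.05 × 0.375 = 0.019 SD, as expected when treated deaths lose the benefit that set 1 would credit to them. The shifts exceed the hand calculation because SD is 3 and the gap is about 16 − 5 = 11: 0.05 × 11/3 = 0.18 SD.

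**The case against.** **Deaths are not hidden.** A reader might infer that the plan conceals a survival difference. It does not: F2 has deaths tracked and serious adverse events compared by arm. The gap is confined to the ADL analyses.

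**The imputation model is unstated.** Survivor-like values are an inference. It is what ordinary imputation does when death is coded as missing, and no death-specific value is planned. The near-exact agreement in the table is partly built in, because the simulated imputation uses the same variables as the ANCOVA. Adding an assumed post-baseline health variable moved set 1 from the complete-case result by about 0.04 to 0.05 points at 3% versus 6% and about 0.07 at 3% versus 8%. Those shifts are small beside 0.18 to 0.30 and 0.30 to 0.50 points, so the logic stands, but exact agreement is not something the documents fix.

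**E1 never says that set 1 tests robustness to deaths.** True; it only contrasts complete cases with imputation, and separating deaths from dropout deserves credit. The point is what agreement could support, not what the authors intended.

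**Deaths may be few.** C4.1 excludes people with conditions that could lead to death within a year and those on chemotherapy or radiation. At 134 per arm, 3% versus 6% is about 4 versus 8 deaths (Fisher p about 0.38). This limits the size of the issue.

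**A composite changes the question** from function to function plus mortality. That is a fair reason to keep it out of the primary analysis, but no bar to a sensitivity analysis.

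**Conclusion.** The point holds for the 20-week ADL analyses in E1. None counts death as unfavourable, and agreement between the imputation sets and the complete-case result would not establish robustness to a survival difference. The size is conditional: about 0.045 to 0.075 SD in either direction at assumed deaths of 3% versus 6% and SD 4, more with a larger imbalance, and small if deaths are few and balanced.

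A reader might go further and infer that the planned analyses favour CAPABLE. The documents do not support that. They give no death rates by arm, and if more deaths fell under usual care the planned analyses would be conservative. Nor does the point undermine the sample size or require a different primary analysis. The claim also does not carry over unchanged to the longitudinal models in E4, where someone who dies between weeks 20 and 52 may still contribute a 20-week score.

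**What to change.** In E1, keep the complete-case primary analysis and set 2. In place of set 1, or beside it, pre-specify one sensitivity analysis before outcomes are examined by arm:

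- Death before the assessment ranks strictly worse than any living Katz score.
- Surviving dropouts are imputed.
- The arms are compared on ranks.
- Deaths by arm are reported next to the ADL result.

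If set 1 is kept, label it a hypothetical estimate in the absence of death, not a test of robustness to deaths, and state its imputation model. Do not use 16 as the death value: the scale runs from 0 to 16, so a death would tie with a living participant at the maximum.

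**Cost.** A few sentences and one extra model. No new data are needed, since set 2 already requires knowing who survived, and the sample size is unchanged. The composite mixes function with mortality, is less direct to read than a mean difference, and may be less precise. As a guide to the last, scoring death as 16 at 3% versus 6% raised the simulated standard error of the difference from about 0.31 to 0.40 points; a rank-based version was not simulated.
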